Appendix C: Data Collection Method

Sponsor/Investigators are required to prepare and maintain adequate and accurate case histories designed to record all observations and other data pertinent to the investigation on each subject 1:1. Source documents include all original records from which eCRF's derive their data.

Worksheet might be provided. The purpose of these worksheets is to aid investigators in the capture of clinical investigational data and ensure all protocol required data, which is not captured in medical records, is recorded to support data for the investigation. These worksheets will not be a copy of the eCRF's, but will contain entry blanks for clinical investigation required data not routinely collected by the investigators.

All documentation pertaining to clinical assessments and medical evaluations should be signed and dated by the appropriate clinical personnel.

Electronic Data Capture (EDC) will be used for this investigation, therefore, please find below instructions on how to access and use the eCRF application.

Access to eCRF application

The eCRF application is accessed through the internet and requires the use of a personal user account and password.

The following documents and information are required prior to receipt of personnel user account and password:

- Current signed and dated CV
- Completed Signature and Delegation List
- Documented training
- Email address and telephone

Personal user account and password are provided via email. User account and password are confidential and personal. They are not to be shared with other people.

The first time the application is accessed, the password will need to be changed.

If the password is forgotten and/or lost, a new password can be provided via email by following the instructions on the webpage.

Each center must be authorized to start enrolling patients in the investigation before access privileges to the application is made available.

Access privileges are based on the tasks assigned on the Signature and Delegation List and will be either:

- Data entry and review
- Data entry, review and sign off

All eCRF's have to be completed, saved ('save complete') and approved by an investigator in a timely manner.

Summary of Casebook Status Icons – Home Page

	No Data Entry is started.
	At least some Data Entry is saved. No Open Discrepancies.
	At least some Data Entry is saved. Active Discrepancy present on at least one CRF requiring current user's attention. May also include Other Discrepancies.
	At least some Data Entry is saved. Other Discrepancy present on at least one CRF requiring current user's attention. No Active Discrepancies present.

Summary of CRF Status Icons – Casebook Page

	CRF not started. Data entry is expected.
	Save Incomplete CRF – The CRF was started and only the Visit Header Date was completed.
	Save Incomplete CRF – Data Entry is incomplete. User is not done inputting all the data, and will finish at a later time.
	Save Complete CRF – Data Entry is complete. User has met all the requirements for the form, and the responses are considered complete. Automated Discrepancy Edit Checks are activated. CRF has no open issues.
	Save Complete CRF – Data Entry is complete. CRF contains Other Discrepancies that another user group must address.
	Save Complete CRF – Data Entry is complete. CRF contains Active Discrepancies that the current user group must address.
	*Approved CRF – CRF Data responses have been approved by an investigator. CRFs must at least be at "Save Complete" status. No Open Discrepancies. (If Open Discrepancies are present, the icon would also be red or yellow.)
	*CRF requires Re-Approval – Looped arrow next to signature indicates Data, an Investigator Comment, and/or Discrepancy was updated since the CRF was Approved. (If Open Discrepancies are present, the icon would also be red or yellow.)
	Verified CRF – CRF Data responses are verified against source documents. CRFs must at least be at "Save Complete" status. No Open Discrepancies. (If Open Discrepancies are present, the icon would also be red or yellow.)
	CRF requires Re-Verification – Looped arrow indicates Data, an Investigator Comment, and/or a Discrepancy was updated since the CRF was Verified. No Open Discrepancies. (If Open Discrepancies are present, the icon would also be red or yellow.)
	CRF requires Re-Verification – Looped arrow indicates Data, an Investigator Comment, and/or a Discrepancy was updated since the CRF was Verified. Active Discrepancies present.
	CRF requires Re-Verification – Looped arrow indicates Data, an Investigator Comment, and/or a Discrepancy was updated since the CRF was Verified. Other Discrepancies present.
	*CRF is Verified and Approved – CRF Data responses are verified against source documents by the FCRA / CRA, and the Data responses approved by the Principal Investigator.
	CRF requires Re-Verification and Re-Approval – Looped arrow indicates Data, an Investigator Comment, and/or a Discrepancy was updated since the CRF was Verified and Approved. Active Discrepancies present.
	*CRF requires Re-Verification and Re-Approval – Looped arrow indicates Data, an Investigator Comment, and/or a Discrepancy was updated since the CRF was Verified and Approved. Other Discrepancies present.
	*CRF requires Re-Verification and Re-Approval – Looped arrow indicates Data, an Investigator Comment, and/or a Discrepancy was updated since the CRF was Verified and Approved. No Open Discrepancies. (If Open Discrepancies are present, the icon would also be red or yellow.)
	CRF at Pass 2 Complete. This icon indicates Data Entry was completed by the sponsor in-house using data submitted on paper CRFs.

*APPROVAL FEATURE CURRENTLY AVAILABLE TO INVESTIGATORS FOR THE DEATH CRF ONLY.

Summary of Discrepancy Status Icons – Data Entry Window (DEW) Navigator Pane

	Active Discrepancy that the current user group must address.
	Other Discrepancy that another user group must address.
	Resolved Discrepancy requiring no further action by any user group.

NOTE: Obsolete Discrepancies due to Data updates or Validation Procedure / Automated Edit Check updates will be removed from the List sub-pane.

Summary of Data Entry Window (DEW) Toolbar Icons

	Add Discrepancy		Delete Row		Approval History		*Print		First/Previous Page		Close
	Investigator Comment		Verification History		Approval		Save		Next/Last Page		

DO NOT USE THESE TOOLBAR FUNCTIONS

Helpful Hints:

- CRF Deletions** – If a CRF with saved data requires deletion notify your SJM contact, providing information about the form.
- Refresh** – Press the "Refresh" button to refresh RDC OnSite with current information (statuses, etc.)
- Printing a Subject Casebook / CRF** – Go to the RDC OnSite Report Page to print a Patient Data Report. Report types include casebooks with saved Subject data and blank Subject casebooks.
- Logout** – Use the web browser close icon "X" to exit. To re-enter, navigate through the SJM Portal.

Version 1.1, September 25, 2009

Version 1.1, September 25, 2009

Appendix D: VARC 2 Endpoints Definitions ¹⁹

Mortality (VARC 2)	
Cardiovascular Mortality: Any one of the following criteria:
 
 • Death due to proximate cardiac cause (e.g., myocardial infarction, cardiac tamponade, worsening heart failure). • Death caused by non-coronary vascular conditions such as neurological events, pulmonary embolism, ruptured aortic aneurysm, dissecting aneurysm, or other vascular disease. • All procedure-related deaths, including those related to a complication of the procedure or treatment for a complication of the procedure. • All valve-related deaths including structural or non-structural valve dysfunction or other valve-related adverse event. • Sudden or witnessed death. • Death of unknown cause. 
Non-Cardiovascular mortality:
 
 • Any death in which the primary cause of death is clearly related to another condition (e.g. trauma, cancer, suicide)
Myocardial Infarction (VARC 2)	
Peri-procedural MI (≤ 72 h after the index procedure) New ischemic symptoms (e.g., chest pain or shortness of breath), or new ischemic signs (e.g. ventricular arrhythmias, new or worsening heart failure, new ST-segment changes, hemodynamic instability, new pathological Q-waves in at least two contiguous leads, imaging evidence of new loss of viable myocardium or new wall motion abnormality), Elevated cardiac biomarkers (preferably CK-MB) within 72 h after the index procedure AND consisting of at least one sample post-procedure with a peak value exceeding 15× as the upper reference limit for troponin or 5× for CK-MB. If cardiac biomarkers are increased at baseline (>99th percentile), a further increase in at least 50% post-procedure is required AND the peak value must exceed the previously stated limit.
 
Spontaneous MI (>72 h after the index procedure) Any one of the following criteria:
 
 • Detection of rise and/or fall of cardiac biomarkers (preferably troponin) with at least one value above the 99th percentile URL, together with evidence of myocardial ischemia with at least one of the following: 
 ○ Symptoms of ischemia ○ ECG changes indicative of new ischemia [new ST-T changes or new Left Bundle Branch Block (LBBB)] ○ New pathological Q waves in at least two contiguous leads ○ Imaging evidence of new loss of viable myocardium or new wall motion abnormality • Sudden, unexpected cardiac death, involving cardiac arrest, often with symptoms suggestive of myocardial ischemia, and accompanied by presumably new ST-segment elevation, or new LBBB, and/or evidence of fresh thrombus by coronary angiography and/ or at autopsy, but death occurring before blood samples could be obtained, or at a time before the appearance of cardiac biomarkers in the blood. • Pathological findings of an acute myocardial infarction.


Stroke and TIA (VARC 2)
	
Diagnostic criteria
 
 • Acute episode of a focal or global neurological deficit with at least one of the following: change in level of consciousness, hemiplegia, hemiparesis, numbness or sensory loss affecting one side of the body, dysphasia or aphasia, haemianopia, amaurosis fugax, or other neurological signs or symptoms consistent with stroke. • Stroke: duration of a focal or global neurological deficit ≥ 24h; OR < 24h, if available neuroimaging documents a new hemorrhage or infarct; OR the neurological deficit results in death. • TIA: duration of a focal or global neurological deficit < 24h, any variable neuroimaging does not demonstrate a new hemorrhage or infarct. • No other readily identifiable non-stroke cause for the clinical presentation (e.g. brain tumor, trauma, infection, hypoglycaemia, peripheral lesion, pharmacological influences) to be determined by or in conjunction with the designated neurologist^a. • Confirmation of the diagnosis by at least one of the following: 
 ○ Neurologist or neurosurgical specialist ○ Neuroimaging procedure (CT scan or brain MRI), but stroke may be diagnosed on clinical grounds alone. 
Stroke classification
 
 • Ischaemic: an acute episode of focal cerebral, spinal, or retinal dysfunction caused by infarction of the central nervous system tissue. • Haemorrhagic: an acute episode of focal or global cerebral or spinal dysfunction caused by intraparenchymal, intraventricular, or subarachnoid haemorrhage. • A stroke may be classified as undetermined if there is insufficient information to allow categorization as ischaemic or haemorrhagic. 
Stroke definitions^b
 
 • Disabling stroke: an mRS score of 2 or more at 90 days and an increase in at least one mRS category from an individual's pre-stroke baseline. • Non-disabling stroke: an mRS score of < 2 at 90 days or one that does not result in an increase in at least one mRS category from an individual's pre-stroke baseline 
^a Patients with non-focal global encephalopathy will not be reported as a stroke without unequivocal evidence based upon neuroimaging studies (CT scan or Brain MRI)
 
^bModified Rankin Score assessments should be made by qualified individuals according to a certification process.


Bleeding (VARC 2)
	
Life-threatening or disabling bleeding
 
 • Fatal bleeding (BARC(22) type 5) OR • Bleeding in a critical organ, such as intracranial, intraspinal, intraocular, or pericardial necessitating pericardiocentesis, or intramuscular with compartment syndrome (BARC type 3b and 3c) OR • Bleeding causing hypovolemic shock or severe hypotension requiring vasopressors or surgery (BARC type 3b) OR • Overt source of bleeding with drop in hemoglobin ≥ 5 g/dl or whole blood or packed red blood cells (RBCs) transfusion ≥ 4 Units^a (BARC type 3b). 
^aGiven 1 U of packed RBC typically will raise blood hemoglobin concentration by 1 g/dl, an estimated decrease in hemoglobin will be calculated.
 
Major bleeding (BARC type 3a)
 
 • Overt bleeding either associated with a drop in the hemoglobin level of at least

	
3.0 g/dl or requiring transfusion of two or three units of whole blood/ RBC, or causing hospitalization or permanent injury, or requiring surgery AND
 
 Does not meet criteria of life-threatening or disabling bleeding 
Minor bleeding (BARC type 2 or 3a, depending on the severity)
 
 Any bleeding worthy of clinical mention (e.g., access site hematoma) that does not qualify as life-threatening, disabling or major.

Acute Kidney Injury AKIN classification (VARC 2)
	
Stage 1 Increase in serum creatinine to 150% - 199% (1.5 to 1.99 X increase compared with baseline) OR increase of ≥ 0.3 mg/dl (≥ 26.4 mmol/l) OR Urine output <0.5 mL/kg/h for >6h but <12h
 
Stage 2 Increase in serum creatinine to 200% -299% (2.0 to 2.99 X increase compared with baseline) OR Urine output <0.5 mL/kg/h for >12h but <24h
 
Stage 3 Increase in serum e to $\geq 300\%$ (> 3 X increase compared with baseline) or serum creatinine of ≥ 4.0 mg/dl (≥ 354 mmol/l) with an acute increase of at least 0.5 mg/dl (44 mmol/l) OR Urine output <0.3 mL/kg/h for ≥ 24h OR Anuria for ≥ 12h
 
Patients receiving renal replacement therapy are considered to meet Stage 3 criteria irrespective of other criteria.


Vascular access Site and Access-Related complications (VARC 2)
	
Major vascular complications
 
 Any aortic dissection, aortic rupture, annulus rupture, left ventricle perforation, or new apical aneurysm/pseudo-aneurysm OR Access site or access-related vascular injury (dissection, stenosis, perforation, rupture, arterio-venous fistula, pseudoaneurysm, hematoma, irreversible nerve injury, compartment syndrome, percutaneous closure device failure) leading to death, life-threatening or major bleeding^a, visceral ischemia or neurological impairment OR Distal embolization (non-cerebral) from a vascular source requiring surgery or resulting in amputation or irreversible end-organ damage OR The use of unplanned endovascular or surgical intervention associated with death, major bleeding, visceral ischaemia or neurological impairment OR Any new ipsilateral lower extremity ischaemia documented by patient symptoms, physical exam, and/or decreased or absent blood flow on lower extremity angiogram OR Surgery for access site-related nerve injury OR Permanent access site-related nerve injury 
Minor vascular complications
 
 Access site or access-related vascular injury (dissection, stenosis, perforation, rupture, arterio-venous fistula, pseudoaneuysms, hematomas , percutaneous closure device failure) not leading to death, life-threatening or major bleeding^a, visceral ischaemia, or neurological impairment OR Distal embolization treated with embolectomy and/or thrombectomy and not resulting in amputation or irreversible end-organ damage OR Any unplanned endovascular stenting or unplanned surgical intervention not meeting the criteria for a major vascular complication OR

- Vascular repair or the need for vascular repair (via surgery, ultrasound-guided compression, transcatheter embolization, or stent-graft)
-

Percutaneous close device failure

- Failure of a closure device to achieve haemostasis at the arteriotomy site leading to alternative treatment (other than manual compression or adjunctive endovascular ballooning)

^aRefers to VARC 2 bleeding definitions


Other TAVI-related complications (VARC 2)
	
Conversion to open surgery
 
 Conversion to open sternotomy during the TAVI procedure secondary to any procedure-related complications 
Unplanned use of cardiopulmonary bypass (CPB)
 
 Unplanned use of CPB for haemodynamic support at any time during the TAVI procedure 
Coronary obstruction
 
 Angiographic or echocardiographic evidence of a new, partial or complete, obstruction of a coronary ostium, either by the valve prosthesis itself, the native leaflets, calcifications, or dissection, occurring during or after the TAVI procedure 
Ventricular septal perforation
 
 Angiographic or echocardiographic evidence of a new septal perforation during or after the TAVI procedure 
Mitral valve apparatus damage or dysfunction
 
 Angiographic or echocardiographic evidence of new damage (chordae papillary muscle, or to the leaflet) to the mitral valve apparatus or dysfunction (e.g. restrictions due to the THV) of the mitral valve during or after the TAVI procedure 
Cardiac tamponade
 
 Evidence of a new pericardial effusion associated with haemodynamic instability and clearly related to the TAVI procedure 
Endocarditis Any one of the following
 
 Fulfilment of the Duke endocarditis criteria (23) Evidence of abscess, paravalvular leak, pus, or vegetation confirmed as secondary to infection by histological or bacteriological studies during a re-operation Findings of abscess, pus, or vegetation involving a repaired or replaced valve during an autopsy 
Valve thrombosis
 
 Any thrombus attached to or near an implanted valve that occludes part of the blood flow path, interferes with valve function, or is sufficiently large to warrant treatment. Note that valve-associated thrombus identified at autopsy in a patient whose cause of death was not valve-related should not be reported as valve thrombosis 
Valve malpositioning
 
 Valve migration : After initial correct positioning, the valve prosthesis moves upwards or downwards, within the aortic annulus from its initial position, with or without consequences Valve embolization: The valve prosthesis moves during or after deployment such that it loses contact with the aortic annulus Ectopic valve deployment : Permanent deployment of the valve prosthesis in a location other than the aortic root 
TAV-in-TAV deployment
 
 An additional valve prosthesis is implanted within a previously implanted prosthesis because of suboptimal device position and/or function, during or after the index procedure

Potential failure modes of prosthetic valve Dysfunction (VARC)
	
Aortic stenosis
 
 Stent creep Pannus Calcification Support structure deformation (out-of-round configuration), under-expansion,

	fracture, or trauma (cardio-pulmonary resuscitation, blunt chest trauma) 
 • Mal-sizing (prosthesis-patient mismatch) • Endocarditis • Prosthetic valve thrombosis • Native leaflet prolapse impeding prosthetic leaflet motion Aortic regurgitation 
 • Pannus • Calcification • Support structure deformation (out-of-round configuration), recoil, under-expansion, fracture, insufficient radial strength, or trauma (cardio-pulmonary resuscitation, blunt chest trauma) • Endocarditis • Prosthetic valve thrombosis • Malposition (too high, too low) • Acute mal-coaptation • Leaflet wear, tear/perforation, prolapse, or retraction • Suture breakage or disruption • Native leaflet prolapse impeding prosthetic leaflet motion 			
Prosthetic Valve Stenosis In conditions of normal or near normal stroke volume (50–70 ml). (VARC 2)	Parameter	Normal	Mild Stenosis	Moderate/Severe Stenosis
	Quantitative parameters (flow-dependent)			
	Peak velocity (m/s)	< 3m/s	3–4m/s	> 4m/s
	Mean gradient (mm Hg)	< 20mmHg	20–40 mmHg	> 40 mmHg
	Doppler velocity index For LVOT >2.5 cm, significant stenosis criteria is <0.20.	> 0.35	0.35–0.25	< 0.25
	Quantitative parameters (flow-independent)			
Effective orifice area (cm ²) Use in setting of BSA ≥1.6 cm ²	> 1.1 cm ²	1.1–0.8 cm ²	< 0.80 cm ²	
Effective orifice area (cm ²) Use in setting of BSA <1.6 cm ² .	> 0.9 cm ²	0.9 – 0.6 cm ²	< 0.6 cm ²	
Prosthesis–patient mismatch (PPM) (VARC 2)	Parameter	Insignificant	Moderate	Severe
	Indexed effective orifice area (cm ² /m ²) Use in setting of BMI <30 kg/ cm ² .	>0.85 cm ² /m ²	0.85–0.65 cm ² /m ²	< 0.65 cm ² /m ²
	Indexed effective orifice area (cm ² /m ²) Use in setting of BMI ≥30 kg/ cm ² .	>0.90 cm ² /m ²	0.90–0.60 cm ² /m ²	< 0.60 cm ² /m ²
Prosthetic	Parameter	Mild	Moderate	Severe

Valve Regurgitation (VARC 2)	Semi quantitative parameters			
	Diastolic flow reversal in the descending aorta—PW	Absent or brief early diastolic	Intermediate	Prominent, holodiastolic
	Circumferential extent of prosthetic valve paravalvular regurgitation (%) Not well-validated and may overestimate the severity compared with the quantitative Doppler.	<10%	10–29%	≥30%
	Quantitative parameters			
	Regurgitant volume (mL/beat)	<30 mL	30–59 mL	≥60 mL
	Regurgitant fraction (%)	<30%	30–49%	≥50%
	EROA (cm ²)	0.10 cm ²	0.10–0.29 cm ²	≥0.30 cm ²
Device Success (VARC 2)	
 • Absence of procedural mortality AND • Correct positioning of a single prosthetic heart valve into the proper anatomical location AND • Intended performance of the prosthetic heart valve (no prosthesis–patient mismatch^a and mean aortic valve gradient <20 mmHg or peak velocity <3 m/s, AND no moderate or severe prosthetic valve regurgitation^a) 			
Early Safety (at 30 days) (VARC 2)	
 • All-cause mortality • All stroke (disabling and non-disabling) • Life-threatening bleeding • Acute kidney injury—Stage 2 or 3 (including renal replacement therapy) • Coronary artery obstruction requiring intervention • Major vascular complication • Valve-related dysfunction requiring repeat procedure (BAV, TAVI, or SAVR) 			
Clinical efficacy (after 30 days) (VARC 2)	
 • All-cause mortality • All stroke (disabling and non-disabling) • Requiring hospitalizations for valve-related symptoms or worsening congestive heart failure^b • NYHA class III or IV • Valve-related dysfunction (mean aortic valve gradient ≥20 mmHg, EOA ≤0.9–1.1 cm²(c) and/or DVI <0.35 m/s, AND/OR moderate or severe prosthetic valve regurgitation^a) 			
Time-related valve safety (VARC 2)	
 • Structural valve deterioration • Valve-related dysfunction (mean aortic valve gradient ≥20 mmHg, EOA ≤0.9–1.1 cm²and/or DVI <0.35 m/s, AND/OR moderate or severe prosthetic valve regurgitation^a) • Requiring repeat procedure (TAVI or SAVR) • Prosthetic valve endocarditis • Prosthetic valve thrombosis • Thrombo-embolic events (e.g. stroke) 			

	
 • VARC bleeding, unless clearly unrelated to valve therapy (e.g. trauma)
	
^arefers to VARC definitions
 
^bAs a basis for calculation of ‘days alive outside the hospital’ endpoint. Supplementary appendix of Leon et al. Includes heart failure, angina, or syncope due to aortic valve disease requiring intervention or intensified medical management; clinical symptoms of CHF with objective signs including pulmonary oedema, hypoperfusion, or documented volume overload AND administration of IV diuresis or inotropic therapy, performance of aortic valvuloplasty, institution of mechanical support (IABP or ventilation for pulmonary oedema) or haemodialysis for volume overload; clear documentation of anginal symptoms AND no clinical evidence that angina was related to CAD or ACS; documented loss of consciousness not related to seizure or tachyarrhythmia.
 
^cDepending on the body surface area.

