5.3 Endpoints

5.3.1 Primary Endpoint

- The primary endpoint is all-cause mortality at 1 year post implant (according to VARC-2¹⁹).

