5.3.2 Secondary Endpoints

- Evaluation of the VARC-2¹⁹ defined event rates at 30 days, 1 year and annually through 5 years post implant. Definitions are detailed in Appendix D: VARC 2 Endpoints Definitions.
 - All-Cause Mortality
 - Cardiovascular Mortality
 - Myocardial Infarction
 - Stroke (disabling and non-disabling)
 - New or worsened conduction disturbances and cardiac arrhythmias (including pacemaker implantation rate at 30 days and new-onset atrial fibrillation (AF))
- Evaluation of the VARC-2¹⁹ defined event rates at 30 days from the index procedure.
 - Vascular access site complication (major and minor)
 - Bleeding (life-threatening, major and minor)
 - Acute kidney injury

- Prosthetic valve function at 30 days, 1 year and annually through 5 years post implant. (Includes prosthetic valve stenosis and prosthetic valve regurgitation).
- Clinical benefit endpoints at 30 days, 1 year and annually through 5 years post implant (if available)
 - NYHA functional classification
 - 6 Minute Walk Test (6MWT)
 - Quality of life measured with EQ-5D questionnaire through 1 year post-implant
- Evaluation of the TAVI-related resource utilization through hospital discharge (e.g. index procedural hospital/physician resources)
- Interim reporting at 30 days and 1-year all-cause mortality data may be performed on a subset of patients and compared with an appropriate external comparator. The results will be presented to appropriate agencies in France and in other countries where it will be deemed necessary for reimbursement purposes.

NOTE: Should new VARC or ESC Guidelines be published, endpoint analysis would be adjusted accordingly and analyzed to the extent that the previously gathered data supports the analyses based on the most current guidelines.

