9.2 Sample size estimation

9.2.1 Cohort A

The sample size estimation is based on the primary endpoint of this study, all-cause mortality at 1 year post implant for patients having received a Portico Valve.

It is assumed that the expected mortality rate at 1 year post implant will be 22.1% ²⁰), and the total recruitment period will be 2 years; at least 608 patients are required to be at risk at 1 year post implant, in order to establish a two sided 95% confidence limit (18.8%, 25.4%) using non-parametric survival analysis with Peto's variance²¹. With a dropout rate of 10%, at least 866 patients need to be recruited.

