14.3.2 Clinical Event Committee

An independent clinical events committee will be established for this clinical investigation. The CEC will include, at a minimum, an interventional cardiologist or a cardiologist, and a cardiothoracic surgeon whose main objective is to review and adjudicate specific adverse events which will occur throughout the duration of this trial, as specified in a separate CEC charter. The CEC will adjudicate these safety related events according to the VARC 2 criteria.

The CEC charter will be established for the CEC member's activities and will be available upon request.

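### In Appendix D a witnessed death from a clear non-cardiovascular cause meets both mortality definitions, with no rule on which prevails; literal use can only raise the cardiovascular rate

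*Combined protocol and SAP*

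**What the plan says.** Cardiovascular mortality is a secondary endpoint, reported at 30 days and at 1, 2, 3, 4 and 5 years. Section 5.3.2 sends the reader to the appendix for its meaning: "Definitions are detailed in Appendix D: VARC 2 Endpoints Definitions". Section 9.4 estimates the safety secondary endpoints by non-parametric survival analysis at each time point.

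The Mortality row of Appendix D opens the cardiovascular list with "Any one of the following criteria". Two of the criteria are "Sudden or witnessed death" and "Death of unknown cause". Directly below the list, non-cardiovascular mortality is defined as "Any death in which the primary cause of death is clearly related to another condition (e.g. trauma, cancer, suicide", with the bracket closing after the examples. Nothing says that the two classes exclude each other, or which governs when both apply.

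Section 14.3.2 sets up an independent events committee: "The CEC will adjudicate these safety related events according to the VARC 2 criteria". The list of events it handles is left to a separate charter.

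The primary endpoint does not use cause of death. Section 5.3.1: "The primary endpoint is all-cause mortality at 1 year post implant".

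**The concern.** Whether a death was witnessed says nothing about its cause. Because one criterion is enough, a patient who dies of cancer with staff or family present satisfies the cardiovascular definition. The same patient also satisfies the non-cardiovascular definition, which names cancer. Two people who both follow the appendix can classify that death differently, and neither would be in breach of the plan.

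Any error has a known direction. The criterion adds deaths to the cardiovascular class and removes none. A rate built on the literal reading would lie between the rate based on cause and the all-cause rate, and it would be hard to compare with cardiovascular mortality reported under another definition.

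**Working it through.** **Step 1: logic of the definitions.** Take three deaths and apply Appendix D as printed.

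| Death | Cardiovascular list | Non-cardiovascular line |
|---|---|---|
| Cancer, witnessed | met (witnessed) | met (cancer) |
| Trauma, sudden | met (sudden) | met (trauma) |
| Cancer, neither sudden nor witnessed | not met | met |

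The first two rows fall in both classes, and the documents contain no tie-break. The list also holds other criteria that do not rest on a cardiac or vascular diagnosis: procedure-related deaths and deaths of unknown cause. A reader therefore cannot assume that a known non-cardiovascular cause automatically overrides the list.

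**Step 2: the plan's own figure.** The documents state no expected cardiovascular mortality, so there is no figure for this endpoint to reproduce. The nearest is the all-cause assumption in Section 9.2.1, "expected mortality rate at 1 year post implant will be 22.1" per cent, with 608 patients at risk and limits of 18.8% and 25.4%. A simple normal approximation gives 1.96 × √(0.221 × 0.779 / 608) = 0.033, hence 18.8% to 25.4%, which agrees. It serves here as a ceiling and a scale.

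**Step 3: illustration of size.** Let *s* be the share of deaths with a clear non-cardiovascular cause and *w* the share of those that are witnessed. The documents give neither; both are assumptions.

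- Rate by cause: 22.1% × (1 − *s*)
- Rate if the cardiovascular line always prevails: 22.1% × [(1 − *s*) + *s* × *w*]
- Shift: 22.1% × *s* × *w*

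| *s* | *w* | By cause | Literal | Shift (points) |
|---|---|---|---|---|
| 30% | 50% | 15.5% | 18.8% | 3.3 |
| 30% | 80% | 15.5% | 20.8% | 5.3 |
| 40% | 50% | 13.3% | 17.7% | 4.4 |
| 40% | 80% | 13.3% | 20.3% | 7.1 |

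With wider assumptions, the shift is 22.1% × 0.20 × 0.50 = 2.2 points at the low end (*s* = 20%, *w* = 50%) and 22.1% × 0.50 × 1.00 = 11.05 points at the high end (*s* = 50%, *w* = 100%). At *w* = 100% the literal rate equals the all-cause rate.

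In deaths, if 22.1% is applied to all 866 planned Cohort A patients: 866 × 0.221 = 191; 191 × 0.30 × 0.50 = 29; 191 × 0.40 × 0.80 = 61. These counts are on the high side, because 866 includes a dropout allowance and Section 9.1 leaves patients who were not implanted out of the analysis. The shift in points does not depend on the number of patients.

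**Step 4: the other branch.** If adjudicators let the non-cardiovascular line prevail whenever another cause is clear, these deaths add nothing and the shift is 0.

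**The case against.** The strongest reply is that the appendix already answers the question. The non-cardiovascular line names trauma, cancer and suicide, and a sensible adjudicator would put a witnessed cancer death there. The synopsis and Section 14.3.2 provide central, independent adjudication, so differences between sites should be limited. The endpoint is descriptive, with no test or threshold attached.

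Much of this stands. A reader might infer that cardiovascular mortality in this trial is inflated. The documents do not support that: they do not say the cardiovascular line prevails, and under the other reading the inflation is zero. Nor do they show that sites will diverge or that the error will grow each year. What does not stand is that adjudication removes the defect. The committee is directed to the VARC 2 criteria, Appendix D is the only statement of those criteria in the documents, and nothing says that the charter corrects the wording or that every death is referred to it.

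A reader might also infer that one wrong word is the whole problem. It is not. With *unwitnessed* in place, a patient with known cancer who dies alone would still meet both definitions, as would a sudden trauma death.

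A prefix lost when the PDF was read cannot be excluded, but nothing shows it. The overlap would remain in any case.

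**Conclusion.** The point holds as a defect in a governing definition: two classes that should be exclusive overlap, with no precedence rule. Any resulting error in cardiovascular mortality can only be upward. Its size at 1 year runs from zero, if a clear other cause prevails, to about 3 to 7 percentage points, if the cardiovascular line prevails. The upper branch rests on the plan's 22.1% all-cause rate and on two assumed shares (30-40% non-cardiovascular, 50-80% of those witnessed). For scale, 3.3 points is the half-width planned for the primary estimate.

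The all-cause primary endpoint, its sample size and its confidence limits are untouched. Severity is moderate: it should be corrected, but it does not threaten the main result.

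**What to change.** 1. Check the criterion against the VARC-2 document cited as reference 19 and correct it. *Unwitnessed* appears to be the intended word, because the adjacent criterion already places deaths of unestablished cause in the cardiovascular class; the sponsor should confirm this from its source.
2. Add a precedence sentence to Appendix D, which does most of the work. Suggested wording: *The two categories are mutually exclusive. A death with a clearly established non-cardiovascular cause, not related to the procedure or the valve, is non-cardiovascular whether or not it was sudden or witnessed.*
3. Put the same wording in the CEC charter and the Death Form guidance.
4. Desk-check deaths already classified, looking for any called cardiovascular only because they were sudden or witnessed.

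The cost is one word, a short precedence statement, matching edits to the supporting documents and a review of existing death records. No new patient data are needed.
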